## **Potential Drug Induced Liver Injury (DILI)**

Specific criteria for identifying potential DILI have not been identified for this protocol. Standard medical practice in identifying and monitoring hepatic issues should be followed.

## **Hospitalization, Prolonged Hospitalization or Surgery**

Any adverse event that results in hospitalization or prolonged hospitalization should be documented and reported as a serious adverse event unless specifically instructed otherwise in this protocol. Any condition responsible for surgery should be documented as an adverse event if the condition meets the criteria for an adverse event.

Neither the condition, hospitalization, prolonged hospitalization, nor surgery are reported as an adverse event in the following circumstances:

- Hospitalization or prolonged hospitalization for diagnostic or elective surgical procedures for a preexisting condition. Surgery should *not* be reported as an outcome of an adverse event if the purpose of the surgery was elective or diagnostic and the outcome was uneventful.
- Hospitalization or prolonged hospitalization required to allow efficacy measurement for the study.
- Hospitalization or prolonged hospitalization for therapy of the target disease of the study, unless it is a worsening or increase in frequency of hospital admissions as judged by the clinical investigator.
- A visit to the emergency room or other hospital department < 24 hours, that does not result in admission (unless considered an important medical or life-threatening event)
- Routine health assessment requiring admission for baseline/trending of health status (e.g., routine colonoscopy)
- Admission encountered for another life circumstance that carries no bearing on health status and requires no medical/surgical intervention (e.g., lack of housing, economic inadequacy, caregiver respite, family circumstances, administrative reason).

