#### **Adverse Event**

An *adverse event* (AE) is any symptom, sign, illness or experience that develops or worsens in severity during the course of the study. Intercurrent illnesses or injuries should be regarded as adverse events. Abnormal results of diagnostic procedures are considered to be adverse events if the abnormality:

- results in study withdrawal
- is associated with a serious adverse event
- is associated with clinical signs or symptoms
- leads to additional treatment or to further diagnostic tests
- is considered by the investigator to be of clinical significance

An Adverse Event (AE) is defined as any new untoward medical occurrence or worsening of a preexisting medical condition in a clinical investigation participant administered study drug and that does not necessarily have a causal relationship with this treatment. An AE can therefore be any unfavorable and unintended sign (such as an abnormal laboratory finding), symptom, or disease temporally associated with the use of investigational product, whether or not considered related to the investigational product.

The causal relationship to study drug is determined by a physician and should be used to assess all adverse events (AE). The causal relationship can be one of the following:

Related: There is a reasonable causal relationship between study drug administration and the AE.

Not related: There is not a reasonable causal relationship between study drug administration and the AE.

The term "reasonable causal relationship" means there is evidence to suggest a causal relationship.

Adverse events can be spontaneously reported or elicited during open-ended questioning, examination, or evaluation of a subject. (In order to prevent reporting bias, subjects should not be questioned regarding the specific occurrence of one or more AEs.)

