### **Serious Adverse Event**

Adverse events are classified as serious or non-serious. A *serious adverse event* is any AE that is:

- fatal
- life-threatening (defined as an event in which the participant was at risk of death at the time of the event; it does not refer to an event which hypothetically might have caused death if it were more severe)
- requires or prolongs hospital stay
- results in persistent or significant disability or incapacity
- a congenital anomaly or birth defect
- an important medical event (defined as a medical event(s) that may not be immediately life-threatening or result in death or hospitalization but, based upon appropriate medical and scientific judgment, may jeopardize the subject or may require intervention [eg, medical, surgical] to prevent one of the other serious outcomes listed in the definition above.) Examples of such events include, but are not limited to, intensive treatment in an emergency room or at home for allergic bronchospasm; blood dyscrasias or convulsions that do not result in hospitalization.)
- Suspected transmission of an infectious agent (eg, pathogenic or nonpathogenic) via the study drug is an SAE.

Important medical events are those that may not be immediately life threatening, but are clearly of major clinical significance. They may jeopardize the subject, and may require intervention to prevent one of the other serious outcomes noted above. For example, drug overdose or abuse, a seizure that did not result in in-patient hospitalization, or intensive treatment of bronchospasm in an emergency department would typically be considered serious.

Although pregnancy, overdose, potential drug-induced liver injury (DILI), and cancer are not always serious by regulatory definition, these events must be handled as SAEs.

Any component of a study endpoint that is considered related to study therapy should be reported as an SAE (e.g., death is an endpoint, if death occurred due to anaphylaxis, anaphylaxis must be reported).

All adverse events that do not meet any of the criteria for serious should be regarded as *non-serious adverse events*.

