### 7.1 *Recording of Adverse Events*

At each contact with the subject, the investigator must seek information on adverse events by specific questioning and, as appropriate, by examination. Information on all adverse events should be recorded immediately in the source document, and also in the appropriate adverse event module of the case report form (CRF). All clearly

related signs, symptoms, and abnormal diagnostic procedures results should be recorded in the source document, though should be grouped under one diagnosis.

All adverse events occurring during the study period must be recorded. The clinical course of each event should be followed until resolution, stabilization, or until it has been determined that the study treatment or participation is not the cause. Serious adverse events that are still ongoing at the end of the study period must be followed up to determine the final outcome. Any serious adverse event that occurs after the study period and is considered to be possibly related to the study treatment or study participation should be recorded and reported immediately.

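### Section 7.1 exempts the condition behind a short emergency or hospital visit without admission from adverse event reporting, which conflicts with the protocol's own rules that non-serious adverse events are collected and recorded

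*Combined protocol and SAP*

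**What the plan says.** The paragraph on hospitalization and surgery in section 7.1 opens with the rule that an adverse event leading to hospitalization is a serious adverse event. It then gives a list of exemptions, introduced by: "Neither the condition, hospitalization, prolonged hospitalization, nor surgery are reported as an adverse event in the following circumstances". Six circumstances follow. The fourth is: "A visit to the emergency room or other hospital department < 24 hours, that does not result in admission", qualified by "unless considered an important medical or life-threatening event".

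The general rules are elsewhere in section 7:

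- The Adverse Event definition in 7.1 says: "Intercurrent illnesses or injuries should be regarded as adverse events". It also covers "any new untoward medical occurrence or worsening of a preexisting medical condition in a clinical investigation participant administered study drug". It makes no exception for where or for how long the patient was treated.
- The Serious Adverse Event definition in 7.1 leaves no gap between the two classes: "All adverse events that do not meet any of the criteria for serious should be regarded as" non-serious adverse events.
- The subsection on collecting non-serious events requires all of them to be collected, whether or not they are thought to be related, from the start of study drug until at least 30 days after the last dose.
- The section on recording (a second section numbered 7.1) says: "All adverse events occurring during the study period must be recorded".

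**The concern.** The lead-in to the exemptions names the condition itself, not only the admission or visit, and it speaks of an adverse event, not a serious one. Read literally, it takes the underlying illness or injury out of adverse event reporting. The general rules keep it in.

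Two reporting routes depend on the answer. Non-serious events go to the funder in aggregate, through interim or final study reports or annual reporting. Section 7.2.2 also requires expedited IRB reporting of any adverse event judged unexpected and related to the research procedures, whether serious or not. An event that staff have been told not to report as an adverse event may reach neither.

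This is an open-label, single-centre study of 25 patients with no comparator, so its safety summary consists of absolute counts. Section 7.4.1 states that there is no independent safety board, and section 9.1 gives the monitoring plan as not applicable. Little else in the plan would catch a gap in event reporting.

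**Working it through.** No formula applies, and the plan states no figure to reproduce. The check is to take one event through each rule.

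**Test case.** A patient has a new infection or injury after the first infusion, within the collection window. It is treated in an emergency department in under 24 hours without admission, and is judged neither medically important nor life-threatening.

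| Rule (section 7) | Result for the test case |
|---|---|
| Adverse Event definition | It is an adverse event: a new untoward occurrence and an intercurrent illness or injury |
| Serious Adverse Event definition | No criterion is met, so it is a non-serious adverse event |
| Collection of non-serious events | It is collected |
| Recording of Adverse Events | It is recorded in the source document and the case report form |
| Hospitalization paragraph, fourth exemption | The condition is not reported as an adverse event |

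The first four rules agree with each other. The fifth does not fit with them unless reporting is held to be a separate step from recording, which is taken up under the objection.

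**What the carve-out keeps.** It keeps medically important and life-threatening events, and both are already seriousness criteria in section 7.1. The events that the exemption removes are therefore non-serious ones. A carve-out of this kind makes sense in a list of exceptions to serious status, which suggests that the lead-in uses the wrong term.

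**The other five exemptions.** Elective or diagnostic procedures for a preexisting condition, admission for efficacy measurement, routine health assessment and social admission do not normally involve a new untoward event. The target-disease exemption keeps worsening reportable. The short-visit exemption is the one that clearly reaches new illness and injury.

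**Precedence.** The protocol does not say whether the general definition or the specific exemption governs, so a site could reasonably follow either.

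**The case against.** The strongest defence is that reported does not mean recorded. The hospitalization paragraph governs what is reported, and its opening sentences use documenting as a separate word. The recording section requires every adverse event to be entered at once in the source document and the case report form, without exception. On that reading the event is captured and both rules can be followed. This is a fair reading of data capture, but it does not remove the conflict. An event that is recorded and then not reported as an adverse event would still be absent from the aggregate reports to the funder and from the IRB route in 7.2.2.

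A second defence is that the list is plainly meant to limit serious-event reporting only. The heading and the opening rule make that likely. The wording still says otherwise, and if that is the intent, the correction changes nothing that the sponsor wants.

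A reader might also infer more than the documents support:

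- *All short emergency visits drop out.* They do not. The exemption requires that there is no admission and does not apply to medically important or life-threatening events.
- *Serious infusion reactions are lost.* They are not. The Serious Adverse Event definition gives intensive emergency treatment of allergic bronchospasm as an example of a serious event, and section 7.2.1 asks for a serious-event report wherever seriousness is in doubt.
- *The more severe non-serious events are lost selectively.* Need for emergency care suggests this, but the documents contain no severity grading to establish it.
- *Nothing in the data would show the omission.* The recording rule means that the source document and case report form may well show it.
- *The loss can be put in percentage points.* One patient is 1/25 = 4% of the sample, but the patient-level incidence falls by that amount only if the patient has no other reported event. The number of such patients would be pure assumption.

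**Conclusion.** The conflict holds, and the lead-in is wrong as written. A non-serious illness or injury treated in a short emergency or hospital visit without admission must be collected and recorded as an adverse event under four rules, yet is exempt from being reported as one under a fifth. The consequence is possible under-counting of non-serious events in the aggregate reports and possible non-reporting to the IRB of events that are unexpected and related.

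The size cannot be computed, because the documents give no rate for such visits. The conclusion rests only on the wording and on the absence of a stated order of precedence. Serious-event, pregnancy and overdose reporting are not affected. No efficacy endpoint or planned test depends on these events: section 3.4 defines no endpoint based on adverse events, and section 6.2 plans no analysis of them. This is a drafting fault in safety reporting, not a flaw in the design.

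**What to change.** Reconcile the passages within section 7. In the lead-in to the exemption list, change the end of the statement so that the listed circumstances are not *reported as a serious adverse event because of the hospitalization, visit or surgery alone*. Then add a sentence: *The underlying condition is still recorded and reported as a non-serious adverse event if it meets the adverse event definition in section 7.1.* The six circumstances themselves can stay as they are.

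If the sponsor does intend to exclude these conditions from adverse event reporting altogether, the definition, collection and recording rules would all have to state that exception, and the safety report would have to disclose it. The first option is simpler and keeps the data.

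The cost is a short protocol amendment and a few more non-serious event entries.

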## Pregnancy

If, following initiation of the investigational product, it is subsequently discovered that a study participant is pregnant or may have been pregnant at the time of investigational product exposure, including during at least 5 half-lives after product administration, the investigational product will be permanently discontinued in an appropriate manner (e.g., dose tapering if necessary for participant).

The investigator must immediately notify [contact] of this event via either the CIOMS, MedWatch or appropriate Pregnancy Surveillance Form in accordance with SAE reporting procedures.

Protocol-required procedures for study discontinuation and follow-up must be performed on the participant.

Follow-up information regarding the course of the pregnancy, including perinatal and neonatal outcome and, where applicable, offspring information must be reported on the CIOMS, MedWatch, BMS Pregnancy Surveillance Form, or approved site SAE form. A BMS Pregnancy Surveillance Form may be provided upon request.

Any pregnancy that occurs in a female partner of a male study participant should be reported to BMS. Information on this pregnancy will be collected on the Pregnancy Surveillance Form. In order for Sponsor or designee to collect any pregnancy surveillance information from the female partner, the female partner must sign an informed consent form for disclosure of this information.

## Overdose

An overdose is defined as the accidental or intentional administration of any dose of a product that is considered both excessive and medically important. All occurrences of overdose must be reported as an SAE.

## Other Safety Considerations

Any significant worsening noted during interim or final physical examinations, electrocardiograms, X-rays, and any other potential safety assessments, whether or not these procedures are required by the protocol, should also be recorded as a non-serious or serious AE, as appropriate, and reported accordingly.

### 7.1 *Recording of Adverse Events*

At each contact with the subject, the investigator must seek information on adverse events by specific questioning and, as appropriate, by examination. Information on all adverse events should be recorded immediately in the source document, and also in the appropriate adverse event module of the case report form (CRF). All clearly

related signs, symptoms, and abnormal diagnostic procedures results should be recorded in the source document, though should be grouped under one diagnosis.

All adverse events occurring during the study period must be recorded. The clinical course of each event should be followed until resolution, stabilization, or until it has been determined that the study treatment or participation is not the cause. Serious adverse events that are still ongoing at the end of the study period must be followed up to determine the final outcome. Any serious adverse event that occurs after the study period and is considered to be possibly related to the study treatment or study participation should be recorded and reported immediately.

## ***7.2 Reporting of Serious Adverse Events and Unanticipated Problems***

Investigators and the protocol sponsor must conform to the adverse event reporting timelines, formats and requirements of the various entities to which they are responsible, but at a minimum those events that must be reported are those that are:

- related to study participation,
- unexpected, and
- serious or involve risks to subjects or others

(see definitions, section 8.1).

If the report is supplied as a narrative, the minimum necessary information to be provided at the time of the initial report includes:

• Study identifier

• Study Center

• Subject number

• A description of the event

• Date of onset

	

• Current status

• Whether study treatment was discontinued

• The reason why the event is classified as serious

• Investigator assessment of the association between the event and study treatment

---	--

### **7.2.1 Investigator reporting: notifying the study sponsor**

Any study-related unanticipated problem posing risk of harm to subjects or others, and any type of serious adverse event, must be reported to the study sponsor by telephone within 24 hours of the event. To report such events, a Serious Adverse Event (SAE) form must be completed by the investigator and faxed to the study sponsor within 24 hours. The investigator will keep a copy of this SAE form on file at the study site. Report serious adverse events by phone and facsimile to:

#### **24-hr Emergency [contact]

Within the following 48 hours, the investigator must provide further information on the serious adverse event or the unanticipated problem in the form of a written narrative. This should include a copy of the completed Serious Adverse Event form, and any other diagnostic information that will assist the understanding of the event. Significant new information on ongoing serious adverse events should be provided promptly to the study sponsor

#### Investigator Reporting to BMS

- All Serious Adverse Events (SAEs) that occur following the subject's written consent to participate in the study through 30 days of discontinuation of dosing must be reported to BMS Worldwide Safety, whether related or not related to study drug. If applicable, SAEs must be collected that relate to any later protocol-specified procedure (e.g., a follow-up skin biopsy).
- Following the subject's written consent to participate in the study, all SAEs, whether related or not related to study drug, are collected, including those thought to be associated with protocol-specified procedures. The investigator should report any SAE occurring after these aforementioned time periods, which is believed to be related to study drug or protocol-specified procedure.
- An SAE report should be completed for any event where doubt exists regarding its seriousness;
- If the investigator believes that an SAE is not related to study drug, but is potentially related to the conditions of the study (such as withdrawal of previous therapy or a complication of a study procedure), the relationship should be specified in the narrative section of the SAE Report Form.
- If the BMS safety address is not included in the protocol document (eg, multicenter studies where events are reported centrally), the procedure for safety reporting must be reviewed/approved by the BMS Protocol Manager. Procedures for such reporting must be reviewed and approved by BMS prior to study activation.

An appropriate SAE form (e.g. ex-US = CIOMS form or USA = Medwatch form) should be used to report SAEs to BMS. If you prefer to use your own Institutional form, it must be reviewed by BMS prior to study initiation. Note: Please include the BMS Protocol number on the SAE form or on the cover sheet with the SAE form transmission.

- The CIOMS form is available at:  
<http://www.cioms.ch/index.php/cioms-form-i>
- The MedWatch form is available at: [MedWatch 3500 Form](#)

- [[contact]](mailto:[contact])
- In accordance with local regulations, BMS will notify investigators of all reported SAEs that are suspected (related to the investigational product) and unexpected (ie, not previously described in the IB). An event meeting these criteria is termed a Suspected, Unexpected Serious Adverse Reaction (SUSAR). Investigator notification of these events will be in the form of a SUSAR Report.
  - Other important findings which may be reported by BMS as an Expedited Safety Report (ESR) include: increased frequency of a clinically significant expected SAE, an SAE considered associated with study procedures that could modify the conduct of the study, lack of efficacy that poses significant hazard to study subjects, clinically significant safety finding from a nonclinical (eg, animal) study, important safety recommendations from a study data monitoring committee, or sponsor decision to end or temporarily halt a clinical study for safety reasons.
  - Upon receiving an ESR from BMS, the investigator must review and retain the ESR with the IB. Where required by local regulations or when there is a central IRB/IEC for the study, the sponsor will submit the ESR to the appropriate IRB/IEC. The investigator and IRB/IEC will determine if the informed consent requires revision. The investigator should also comply with the IRB/IEC procedures for reporting any other safety information.
  - In addition to the Sponsor Investigator's responsibility to report events to their local HA, suspected serious adverse reactions (whether expected or unexpected) shall be reported by BMS to the relevant competent health authorities in all concerned countries according to local regulations (either as expedited and/or in aggregate reports).

SAEs, whether related or not related to study drug, and pregnancies must be reported to BMS within 24 hours \ 1 Business Day of becoming aware of the event. SAEs must be recorded on either CIOMS, MedWatch, or approved site SAEform.

Pregnancies must be reported and submitted to BMS on any of the following form(s):

1. MedWatch or, CIOMS or
2. BMS Pregnancy Surveillance Form or,
3. Approved site SAE form

**SAE Email Address:** [contact]

**SAE [contact]

If only limited information is initially available, follow-up reports are required. (Note: Follow-up SAE reports should include the same investigator term(s) initially reported.)

If an ongoing SAE changes in its intensity or relationship to study drug or if new information becomes available, a follow-up SAE report should be sent within 24 hours \ 1 Business Day to BMS using the same procedure used for transmitting the initial SAE report.

All SAEs should be followed to resolution or stabilization.

